## **6.6. Medical History**

For subjects in the ITT and safety population, medical history will be summarized by assigned treatment group. This summation will include the number and percentage of subjects with significant medical history for each body system/organ class and documented on the Medical History CRF.

## **6.7. Prior and Concomitant Medication**

For subjects in the safety population, prior medications and concomitant medications will be coded using the WHO Drug Dictionary and summarized by WHO drug class and WHO drug term. In the data listing, each medication will be recorded as prior, concomitant, or both prior and concomitant. Results will be summarized as number and percentage of subjects with prior and concomitant medications by preferred term and WHO drug class.

Prior medication information will also be used to identify anticancer medication received by subjects before enrollment into the study. Prior anticancer medication data will be summarized and presented by treatment group as well as listed.

## 7. EFFICACY

Sample data displays are provided in [Appendix C](#).

### 7.1. General Considerations

Not applicable.

### 7.2. Efficacy Hypotheses

Not applicable.

### 7.3. Analysis of the Primary Efficacy Parameter

#### 7.3.1. Objective Response Rate

The primary variable for the Phase 2 portion of the study is ORR. Objective disease status will be categorized using mRECIST v1.1. Subjects' objective response will be evaluated as CR, partial response (PR), stable disease (SD), progressive disease (PD), or not evaluable (NE) at each postbaseline radiological assessment based on changes in target lesions, nontarget lesions, and appearance of new lesions.

For subjects with measurable disease at baseline, the mRECIST v1.1 assessment criteria presented in [Table 7](#) can be used to determine the overall response at a given timepoint based on the target lesion, nontarget lesion, and new lesion assessment.

**Table 7: RECIST Evaluation Criteria for Objective Response: Measurable Disease at Baseline**

Target Lesions	Nontarget Lesions	New Lesions	Overall Response
CR	CR (or no nontarget lesion)	No	CR
CR	Non-CR/non-PD	No	PR
CR	NE	No	PR
PR	Non-PD and NE (or no nontarget lesion)	No	PR
SD	Non-PD and NE (or no nontarget lesion)	No	SD
Not all evaluated	Non-PD	No	NE
PD	Any	Yes or No	PD
Any	PD	Yes or No	PD
Any	Any	Yes	PD

PR = partial response.

A subject is considered an objective responder as assessed by mRECIST if they have an overall response of CR or PR at any postbaseline visit. The proportion of responders within each treatment group will be estimated with 95% CIs by treatment group. Confidence intervals will be calculated based on the exact method for binomial distributions.

In general, best response is determined on subject level using the highest overall response achieved postbaseline. In the case of SD, measurements must meet the SD criteria at least once after study entry at a minimum interval of 56 ( $\pm 7$ ) days. Subjects who fail to meet these criteria will have best response of PD if the next available RECIST evaluation after the initial scan indicates PD or NE if there are no additional RECIST evaluations available.

A sensitivity analysis for the primary endpoint will be performed in response evaluable population.

## **7.4. Analysis of Secondary Efficacy Parameters**

### **7.4.1. Objective Response Rate**

One of the secondary variables for the Phase 1 portion of the study is ORR. The definition and analysis for this variable is same as [Section 7.3.1](#).

### **7.4.2. Durability of Response**

For objective responders, the DoR is the time from the first overall response contributing to an objective response (CR or PR) to the earlier of the subject's death or first assessment of PD (for mRECIST v1.1) occurring after the first objective response contributing to the objective response. Median DoR will be estimated using the Kaplan-Meier method. Confidence intervals for median survival time will be calculated using the method of Brookmeyer and Crowley (1982), which is the default method within SAS v9.1. Subjects who are still responding (no PD or death) at the time of database freeze or discontinuation will be right censored at the time of last valid RECIST assessment. The DoR evaluation will be performed separately for each treatment arm and no statistical comparison will be made.

### **7.4.3. Progression-Free Survival**

Progression-free survival is defined as the number of days from enrollment to the earlier of death or disease progression by mRECIST v1.1. Date of death will be determined using the Death Report, the Survival Follow-Up, and the Subject Status CRFs. Censoring for PFS will follow the algorithm outlined in [Table 8](#), which is based on FDA guidance (FDA 2007). Of note, the Protocol mandates radiological evaluation of subjects every 8 weeks after the first dose of study treatment for 12 months (and then every 12 weeks thereafter until disease progression), and radiological evaluation should follow calendar days and not be adjusted for delays in cycle starts or extension of combination treatment cycle frequencies. The analyses will be based on the ITT population, according to treatment group assignment. Time-to-event data will be analyzed by the Kaplan-Meier method. The Kaplan-Meier curve for PFS will be provided.

**Table 8: Evaluation and Censoring of Progression-Free Survival**

Situation	Outcome	Date of Progression or Censoring
No baseline tumor assessments	Censored	Date of randomization
Progression documented between scheduled visits	Progressed	Earliest of: 
 
• Date of radiological assessment showing new lesion (if progression is based on new lesion); or
 
• Date of last radiological assessment of measured lesions (if progression is based on increase in sum of measured lesions)
 

No progression	Censored	Date of last valid radiologic assessment (not NE and not missing)
Treatment discontinuation for undocumented progression	Censored	Date of last valid radiologic assessment (not NE and not missing)
Treatment discontinuation for toxicity or other reason	Censored	Date of last valid radiologic assessment (not NE and not missing)
New anticancer treatment started	Censored	Date of last valid radiologic assessment (not NE and not missing)
Death before first PD assessment	Progressed	Date of death
Death between adequate assessment visits	Progressed	Date of death
Death or progression after more than 1 missed consecutive assessment	Censored	Date of last valid radiologic assessment (not NE and not missing)

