7.4.2. Tumor Imaging During the Study

Tumor assessments will be based on RECIST v1.1 guidelines ([Eisenhauer et al 2009](#)) with modifications for all subjects and will be performed every 12 weeks from the first dose of study treatment (see [Table 24](#)). This assessment schedule also applies to those subjects who continue to receive study treatment beyond confirmed PD (see Section [7.4.3.3.4](#)). Scheduled disease assessments should always be calculated from the first dose of study treatment. Imaging should not be delayed for delays in cycle starts. For those subjects who discontinue study treatment as a result of confirmed PD, disease evaluation will be performed at the EOT visit if clinically appropriate (ie, in the absence of rapidly deteriorating clinical status). Additional disease assessments may be performed as clinically indicated. Images of the chest and abdomen are required for all subjects, and neck imaging is also required for subjects with SCCHN. Imaging of the pelvis is only required for subjects with TCC of the GU tract but is strongly encouraged for all subjects.

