9.4.2. Secondary Analyses

For objective responders, the duration of response is the time from the first overall response contributing to an objective response, to the first overall response of PD (by mRECIST v1.1) occurring after the first overall response contributing to the objective response. Median duration of response and time to disease progression will be estimated using the Kaplan-Meier method. Confidence intervals for median survival time will be calculated using the method of Brookmeyer and Crowley (1982), which is the default method within SAS v9.1.

Progression-free survival data will be analyzed by the Kaplan-Meier method, treating subjects with no observed death or progression censored at their last date known to be alive and progression-free.

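### SAP Table 8 leaves the PFS censoring scan unanchored, so a literal coding would censor a known progression on its own date and bias the PFS rates upward

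*SAP*

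**What the plan says.** SAP 7.4.3 makes Table 8 the governing rule: "Censoring for PFS will follow the algorithm outlined in" that table. It also defines the endpoint: "Progression-free survival is defined as the number of days from enrollment to the earlier of death or disease progression by mRECIST v1.1".

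Five censored rows of Table 8 share one date, "Date of last valid radiologic assessment (not NE and not missing"). Two of them matter here:

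- "Death or progression after more than 1 missed consecutive assessment": outcome censored.
- "Treatment discontinuation for toxicity or other reason": outcome censored.

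Neither row says what the last assessment must precede. The only test of validity is that the scan is not NE and not missing.

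Protocol 9.4.2 has a different rule. Only subjects with no observed death or progression are censored, and they are "censored at their last date known to be alive and progression-free". SAP 10.1 records no change to the protocol-defined analyses.

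**The concern.** A PD scan meets Table 8's test of a valid scan. For a subject whose progression is found after a gap, the last valid scan is then the PD scan itself. The subject would stay in the risk set as event-free through the whole gap and leave without an event on the day progression was documented.

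The discontinuation row is open to the same reading. For subjects stopping without confirmed progression, SAP Table 5 and Protocol Table 24 call for a scan around discontinuation. SAP Table 5 also continues imaging after a stop for reasons other than progression. If one of those scans shows PD, Table 8 does not say whether the discontinuation row still applies or which scan supplies the date.

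What is at stake is the set of Month 3, 6, 9 and 12 PFS rates with confidence intervals in the SAP's Table 2.1.1 and Table 2.1.2 shells. Two programmers could code the rows differently, and one of the two codings biases the rates upward.

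**Working it through.** The documents give no PFS event count, power or expected rate of missed scans, so there is no plan figure to reproduce. The check applies the rules to a worked case and then to assumed inputs.

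**One subject.** 8-weekly scans, valid scan at week 8, weeks 16 and 24 missed, PD at week 32.

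| Rule | Result |
|---|---|
| Protocol 9.4.2 | event at week 32 |
| Table 8, last valid scan before the gap | censored at week 8 |
| Table 8, literal | censored at week 32 |

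**Ten subjects.** Add nine others: two events each at weeks 8, 16 and 24, one each at weeks 32 and 40, and one censored at week 48. Kaplan-Meier at week 32:

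- Event rule: 8/10 × 6/8 × 4/6 × 2/4 = 0.20.
- Pre-gap censoring: 8/10 × 5/7 × 3/5 × 2/3 = 0.229.
- Literal: 8/10 × 6/8 × 4/6 × 3/4 = 0.30.

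**Closed form.** Inputs:

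- Exponential PFS with a median of 3.7 months, or 3.7 × 365.25/12/7 = 16.1 weeks. This is the pembrolizumab NSCLC figure in Protocol 1.1.7, assumed to carry over.
- Scans every 12 weeks (Protocol 7.4.2).
- A fraction f of subjects, assumed, misses weeks 12 and 24 and returns at week 36.

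Let s = S(12) = 2^(−12/16.1) = 0.5965, so true S(36) = s³ = 0.2123.

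- Event rule: S(36) = s³ = 21.2%.
- Literal: nobody leaves the risk set before week 36, so S(36) = 1 − (1 − f)(1 − s³).
- Pre-gap: the f(1 − s³) subjects found with PD at week 36 are censored at time zero, so S(36) = s³ / [1 − f(1 − s³)].

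| f | Literal | Pre-gap | Difference (points) |
|---|---|---|---|
| 3% | 1 − 0.97 × 0.7877 = 23.6% | 0.2123/0.9764 = 21.7% | 1.8 (before rounding) |
| 5% | 1 − 0.95 × 0.7877 = 25.2% | 0.2123/0.9606 = 22.1% | 3.1 |
| 10% | 1 − 0.90 × 0.7877 = 29.1% | 0.2123/0.9212 = 23.0% | 6.1 |

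Nine months is 9 × 365.25/12/7 = 39.1 weeks. On this scan grid the Month 9 rate is therefore the week-36 value. In a 28-subject cohort (Protocol Table 34), one subject is 1/28 = 3.6% and three are 3/28 = 10.7%.

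**Other schedules and medians.** The SAP specifies 8-weekly scans for the first 12 months; the current protocol has 12-weekly. A simulation of 100,000 subjects per scenario, with scans to week 48, covered both. It used medians of 16.1 weeks and 8.6 weeks (the urothelial figure in Protocol 1.1.12). The two scans around progression were missed with assumed probability 5%, 10% or 20%.

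| Scans, median | Week 36 literal (5/10/20%) | Week 36 pre-gap (5/10/20%) |
|---|---|---|
| 8-weekly, 16.1 wk | 28.6 / 32.1 / 39.0% | 26.7 / 28.5 / 32.0% |
| 8-weekly, 8.6 wk | 11.1 / 15.0 / 23.8% | 8.2 / 9.0 / 11.4% |
| 12-weekly, 16.1 wk | 24.6 / 27.8 / 33.9% | 22.2 / 23.2 / 25.0% |
| 12-weekly, 8.6 wk | 9.7 / 14.1 / 22.7% | 5.9 / 6.3 / 7.2% |

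The literal rule was higher at weeks 36 and 48 than both the event rule and pre-gap censoring in all 12 scenarios. The median was the same under literal and pre-gap coding in 11 of 12. The exception was 12-weekly scans, median 8.6 weeks, 20% gaps: 24 against 12 weeks.

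**The case against.** The strongest reply is that Table 8 never names the PD scan as the censoring date. The same phrase serves the row for subjects without progression, where it can only mean a progression-free scan. The endpoint definition and Protocol 9.4.2 both point away from censoring on a PD scan, and SAP 10.1 declares no departure from the protocol. This stands to a degree. A reader might infer that the plan does censor progressions on their own date and that PFS will be overstated. The documents support only that a literal coder could do so. They do not supply the missing anchor either.

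Other limits also stand:

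- The death half of the missed-assessment row is unaffected, because the last scan precedes death.
- The missed-scan rates are assumed. The closed form has subjects miss two scans regardless of disease status and then return.
- No hypothesis test, sample size or decision rule depends on PFS.

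Three further inferences are tempting but weak:

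- **Sum-based PD dated at a later scan.** Table 8 uses the "Date of last radiological assessment of measured lesions (if progression is based on increase in sum of measured lesions"), and Protocol 7.4.2 continues scanning after PD: "This assessment schedule also applies to those subjects who continue to receive study treatment beyond confirmed PD". But that Table 8 row covers progression between scheduled visits and takes the earliest of its listed dates. It can mean the last scan completing one assessment.
- **Scans after new anticancer treatment.** SAP Table 5 stops follow-up imaging when new therapy starts. The main exception is an end-of-treatment scan within its 4-week window.
- **No postbaseline scan.** The screening scan could give a time at or before zero. That is untidy, but such a subject adds nothing to the Kaplan-Meier estimate and does not raise it.

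**Conclusion.** The point holds as an unanchored rule whose literal reading is wrong. For progression after more than one missed assessment, and for PD found around or after discontinuation, Table 8 allows the PD scan to be the censoring date. It also conflicts with Protocol 9.4.2, under which an observed progression after missed scans is an event.

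The direction is upward whenever the literal reading is used. The size cannot be fixed from the documents. It is about 2 to 6 points at week 36 over pre-gap censoring under the closed-form assumptions, and about 2 to 16 points across the wider simulated range. The median usually stays the same. Because PFS is a secondary, descriptive endpoint, no error rate or sample size changes. The wording should still be corrected before the PFS derivation is programmed.

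**What to change.** 1. In the censored rows write: *date of the last valid radiologic assessment showing no progression, before the first of the missed assessments (or on or before the start of new anticancer treatment), or the PFS start date if there is no postbaseline assessment*.
2. State how PD found at or after treatment discontinuation is handled, and which row takes precedence.
3. Reconcile Table 8 with Protocol 9.4.2 on whether progression or death after missed scans is an event. Anchoring alone does not settle this. Report the other choice as a sensitivity analysis.
4. As a minor clarification, state that sum-based PD is dated at the assessment where the criterion was first met.

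The cost is SAP wording, a small change to the PFS derivation and one extra analysis. Reported PFS rates may be slightly lower than under literal coding.

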**7.4.4. Largest Percent Reduction in Sum of Diameters of Target Lesions**

For each subject, the percentage change from baseline in sum of the diameters (shortest diameter is used for lymph nodes, longest diameter for all other target lesions per RECIST v1.1) of target lesions will be derived for each postbaseline period at which a valid target lesion assessment is provided. The best percentage change for each subject will be derived for waterfall plots [REDACTED]

Per RECIST criteria, target lesions considered "too small to measure" will be assigned a default value of 5 mm for purposes of this analysis. Likewise, target lesions identified as "not present" at postbaseline assessments will be assigned 0 mm for this analysis. In the event a target lesion is unaccounted for in a particular postbaseline timepoint, that is, assessment missing or NE, then the overall sum of target lesions will not be evaluable for that postbaseline timepoint.

**7.4.5. Other Efficacy Analyses**

**7.4.5.1. Eastern Cooperative Oncology Group Performance Status**

Subjects' ECOG performance status at scheduled assessment times (see [Table 5](#)) will be summarized in the listings.

### 7.4.5.2. Weight

Subjects' body weight at scheduled assessment times (see [Table 5](#)) will be summarized in the listings.

## 7.5. Pharmacokinetic Analyses

INCB024360 PK in this subject population will be evaluated using noncompartmental analysis and/or population PK modeling.

### 7.5.1. Pharmacokinetic Data

Subject will withhold morning dose of INCB024360 during INCB024360 PK days. The time of last dose of INCB024360 and prior meal will be recorded in the CRF. Pharmacokinetic samples will be obtained at the visits indicated in [Table 6](#). After the predose PK sample is drawn (predose is defined as within 24 hours before administration of MEDI4736 and before administration of INCB024360), subjects will take INCB024360 and then begin infusion of MEDI4736. The exact date and time of the PK blood draws will be recorded in the CRF along with the date and time of the last dose of study drug preceding the blood draw. Sample collection times for INCB024360 are shown in [Table 9](#).

**Table 9: Sample Collection Windows for Pharmacokinetic Assessments for INCB024360**

Study Visit	Timing of Sample Relative to INCB024360 Administration						
Cycle 1 Day 1	Predose	0.5 h ± 10 min	1 h ± 10 min	2 h ± 30 min	4 h ± 30 min	6 h ± 30 min	OPTIONAL 8 to 10 h ± 30 min
Cycle 1 Day 8	Predose	0.5 h ± 10 min	1 h ± 10 min	2 h ± 30 min	4 h ± 30 min	6 h ± 30 min	OPTIONAL 8 to 10 h ± 30 min
Cycle 2 Day 1	Predose	Anytime (required)					

Measurement of MEDI4736 concentrations in serum will be performed using validated immunoassays. Only subjects who receive at least 1 dose of MEDI4736 and provide at least 1 post-treatment sample will be evaluated. Individual MEDI4736 will be tabulated by dose cohort along with descriptive statistics. The following PK parameters after the first and steady-state dose will be estimated (as data allow): peak concentration ( $C_{max}$ ), trough concentration ( $C_{min}$ ), time to maximum observed concentration ( $t_{max}$ ), and AUC. Accumulation to steady state will be assessed as the ratio of  $C_{max,ss} \cdot C_{max}$  and  $C_{min,ss} \cdot C_{min}$ . All PK parameters will be estimated by noncompartmental analysis. Descriptive statistics of noncompartmental PK parameters will be provided.

### 7.5.2. Subject Demographic, Clinical Laboratory, Disease-Related, and Pharmacogenomic Variables and Concomitant Medications

Subject demographic assessments (age, weight, BMI, gender, and race), clinical laboratory measurements (eg, creatinine clearance, serum albumin, total bilirubin, alkaline phosphatase, alanine aminotransferase, aspartate aminotransferase), and the baseline polymorphism of

UGT1A9 may be explored as time-independent predictors of PK variability. Concomitant medications may be explored as covariates in the population PK analysis.

### 7.5.3. INCB024360 Pharmacokinetic Analyses

The noncompartmental analysis for INCB024360 PK will be performed using commercial software such as Phoenix WinNonlin version 6.0 or later (Pharsight Corporation, Mountain View, CA). Nominal times may be used in all cases except when the difference between the actual collection time and the nominal collection time is greater than 15 minutes for samples collected up to 4 hours after administration and greater than 30 minutes for samples collected more than 4 hours after administration. The following 6 PK parameters will be estimated where possible:  $C_{max}$ ,  $T_{max}$ ,  $AUC_{0-t}$ ,  $AUC_{0-12h}$ ,  $t_{1/2}$ , and  $CL/F$  (the latter 3 parameters will only be assessed on C1D8).

For the optional population PK analysis for INCB024360, the data preparation will be performed using SAS version 9.1. [REDACTED]

[REDACTED] Compartment models with first-order absorption and linear elimination will be tested for their ability to characterize the PK of INCB024360. Interindividual variability will be modeled using an exponential error model and explored for each PK parameter. Proportional error, additive error, and mixed additive plus proportional error models will be individually evaluated for their ability to describe the magnitude of residual variability. The first-order conditional estimation method with the interaction option will be used.

After a final base model is identified, covariates will be tested as predictors of PK variability. A generalized additive model analysis will be used as a screening tool to initially identify covariates to be formally tested for statistical significance in NONMEM. The candidate covariates will be incorporated into the PK model as fixed-effect parameters by making the typical values of the structural PK parameters a function of the covariate. NONMEM regression analysis will be performed on the model, with covariate parameters being added in a stepwise univariate fashion during the forward selection process and removed in the model reduction (backward elimination) process. The likelihood ratio test will be used to evaluate the significance of incorporating parameters into or removing parameters from the population model. The accuracy and robustness of the final population PK model will be investigated using a visual predictive check method.

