1.1.13.1. Summary of Epacadostat Pharmacokinetics in Humans

As of 29 OCT 2015, a total of 253 subjects were enrolled and received at least 1 dose of epacadostat in Incyte-sponsored studies, and 47 subjects were enrolled and received at least 1 dose of epacadostat in investigator-sponsored studies.

In Study INCB 24360-101, the multiple-dose PK of epacadostat was evaluated in subjects with refractory solid tumors at doses of 50 mg QD to 700 mg BID. Pharmacokinetic observations include the following and are summarized in Figure 1.

- After oral dose administration in the fasted state, the peak plasma concentration of epacadostat was typically attained at 2 hours postdose. Epacadostat was eliminated with a geometric mean terminal disposition half-life of 2.9 hours.
- Systemic accumulation after BID administration increased the mean epacadostat C_{\max} and AUC_{0-t} by 16% and 33%, respectively, suggesting an "effective" half-life of 4 to 6 hours.
- Increases in epacadostat C_{\max} and AUC_{0-t} were less than proportional to dose. The slightly lower than dose-proportional relationship was most likely because of the limited rate and/or extent of intestinal absorption for this compound at higher doses.
- A high-fat meal delayed epacadostat median T_{\max} by 4 hours but did not cause a clinically significant change in epacadostat plasma exposures. Therefore, epacadostat may be administered without regard to food.
- Moderate intersubject variability was observed for epacadostat plasma exposure at the steady state after administration in the fasted state.
- The highest steady-state mean unbound 0- to 24-hour AUC ($2.2 \mu\text{M}\cdot\text{h}$) observed in this study (700 mg BID dose group) was well below the NOAEL unbound AUC_{0-24h} of $7.9 \mu\text{M}\cdot\text{h}$ observed in the 28-day GLP toxicology study.

Figure 1: Epacadostat Plasma Concentrations (Mean \pm SE) in Cancer Patients Receiving Multiple Doses of Epacadostat in the Fasted State

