7.6.1. Pharmacokinetics

7.6.1.1. Pharmacokinetic Assessment for Epacadostat

Subject will withhold morning dose of drug during PK days. The time of last dose of study medication and prior meal will be recorded in the CRF. Pharmacokinetic samples will be obtained at the visits indicated in [Table 25](#) and [Table 29](#). After the predose PK sample is drawn (predose is defined as within 24 hours before dosing of durvalumab and before dosing epacadostat), subjects will take epacadostat and then begin infusion of durvalumab. The exact

date and time of the PK blood draws will be recorded in the CRF along with the date and time of the last dose of study drug and last meal preceding the blood draw. Sample collection times for epacadostat are shown in [Table 29](#).

Table 29: Sample Collection Windows for Pharmacokinetic Assessments for Epacadostat

Study Visit	Timing of Sample Relative to Epacadostat Administration						
Cycle 1 Day 1 ^a	Predose ^b	0.5 h ± 10 min	1 h ± 10 min	2 h ± 30 min	4 h ± 30 min	6 h ± 60 min	OPTIONAL 8 to 10 h ± 60 min
Cycle 1 Day 8 ^c	Predose ^b	0.5 h ± 10 min	1 h ± 10 min	2 h ± 30 min	4 h ± 30 min	6 h ± 60 min	OPTIONAL 8 to 10 h ± 60 min
Cycle 2 Day 1 ^a	Predose ^b	0.5 h ± 10 min	1 h ± 10 min	2 h ± 30 min	4 h ± 30 min	6 h ± 60 min	OPTIONAL 8 to 10 h ± 60 min

^a ECGs are also required. See [Table 27](#) for timing of ECGs relative to PK sampling. ECGs should be performed before a PK draw.

^b Predose samples should be collected before durvalumab infusions as well.

^c **Only subjects in Phase 1 should have epacadostat PK performed on Cycle 1 Day 8.**

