## LIST OF ABBREVIATIONS

Abbreviation	Term
AE	adverse event
ADA	antidrug antibody
ALT	alanine aminotransferase
aPTT	activated partial thromboplastin time
AST	aspartate aminotransferase
AUC	area under the concentration-time curve
AUC 0-12h	AUC from hour 0 to 12
AUC 0-τ	AUC from time zero (predose) to time of last observed quantifiable concentration within a subject across all treatments
BID	twice daily
CI	confidence intervals
CL/F	apparent oral dose clearance
C max	maximum observed concentration
CR	complete response
CRF	case report form
CSR	Clinical Study Report
CTCAE	Common Terminology Criteria for Adverse Events
DLCO	diffusing capacity of the lung for carbon monoxide
DLT	dose-limiting toxicity
DoR	duration of response
ECG	electrocardiogram
ECOG	Eastern Cooperative Oncology Group
EOT	end of treatment
FDA	Food and Drug Administration
FEF	forced expiratory flow
FEV 1	forced expiratory volume in 1 second
FVC	forced vital capacity
GGT	gamma-glutamyl transferase
HBV-DNA	hepatitis B virus deoxyribonucleic acid
HCV-RNA	hepatitis C virus ribonucleic acid
IDO	indoleamine 2,3-dioxygenase
IgG1κ	human immunoglobulin G1 kappa
INR	international normalized ratio
ITT	intent to treat
IV	intravenously
LFT	liver function tests
LLN	lower limit of normal
MedDRA	Medical Dictionary for Regulatory Activities

Abbreviation	Term
mRECIST v1.1	modified Response Evaluation Criteria in Solid Tumors version 1.1
MTD	maximum tolerated dose
NE	not evaluable
NSCLC	non-small cell lung cancer
ORR	objective response rate
PAD	pharmacologically active dose
PD	██████████ progressive disease
PD-L1	programmed cell-death ligand 1
PFS	progression-free survival
PK	pharmacokinetics
PR	partial response
PT	prothrombin time
RECIST	Response Evaluation Criteria in Solid Tumors
RR	ribonucleotide reductase
SCCHN	squamous cell carcinoma of the head and neck
SD	stable disease
SAE	serious adverse event
SAP	statistical analysis plan
SI	International System of Units
$t_{1/2}$	terminal phase half-life
$T_{max}$	time of occurrence of $C_{max}$
TEAE	treatment-emergent adverse event
ULN	upper limit of normal
VA	alveolar volume
WHO	World Health Organization

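### Epacadostat AUC0-t has no common end time: the sample after 6 h is optional, so equal exposures can give values about 18% to 32% apart

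*SAP*

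**What the plan says.** SAP 7.5.3 lists Cmax, Tmax, AUC0-t, AUC0-12h, half-life and CL/F under the sentence "The following 6 PK parameters will be estimated where possible". It adds that "the latter 3 parameters will only be assessed on C1D8", meaning AUC0-12h, half-life and CL/F.

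The SAP does not define AUC0-t under that symbol. The List of Abbreviations has one entry whose words fit it, printed against AUC0-τ: "AUC from time zero (predose) to time of last observed quantifiable concentration within a subject across all treatments".

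SAP Table 9 requires samples predose and at 0.5, 1, 2, 4 and 6 h on Cycle 1 Days 1 and 8, followed by "OPTIONAL 8 to 10 h ± 30 min". On Cycle 2 Day 1 it requires only a predose sample and one at any time. Protocol Table 29 (Section 7.6.1.1, Amendment 7) gives all three visits the full set of times and ends with "OPTIONAL 8 to 10 h ± 60 min". A footnote to that table limits the Cycle 1 Day 8 profile to Phase 1.

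Neither document sets a common truncation time, a rule for subjects without the late sample, or a summary split by whether it was given.

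**The concern.** An AUC is comparable between subjects only if it covers the same interval. Here the interval depends on an optional draw: AUC0-t is in effect AUC0-6h for a subject who declined it and AUC0-8h to AUC0-10h for one who gave it. SAP 7.5.3 allows nominal times, but the schedule gives the late sample no single nominal time, so even subjects who gave it need not share an endpoint.

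Epacadostat PK parameters are a secondary endpoint in both phases. Because AUC0-12h is restricted to Cycle 1 Day 8, AUC0-t is the only AUC planned at Cycle 1 Day 1. With the current Protocol's full Cycle 2 Day 1 profile it is also the only AUC at that visit, and hence the only one for Phase 2. If uptake of the late draw differs between groups, a group difference in AUC0-t partly reflects that uptake.

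**Working it through.** The documents give no figure for this effect, so there is none to reproduce. I modelled its size.

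**Inputs (Protocol 1.1.13.1).** Tmax is 2 h: "the peak plasma concentration of epacadostat was typically attained at 2 hours postdose". Half-life is 2.9 h: "Epacadostat was eliminated with a geometric mean terminal disposition half-life of 2.9 hours". For sensitivity, the same section infers an effective "half-life of 4 to 6 hours". Sampling times are those of SAP Table 9 and Protocol Table 29.

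**Model.** One compartment with first-order absorption and linear elimination, within the model class SAP 7.5.3 names for population PK.

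- k = ln 2 / 2.9 = 0.239 per h.
- ka solves ln(ka/k)/(ka − k) = 2 h, giving ka = 0.904 per h.
- Single dose, up to a scale factor that cancels in ratios: C(t) = exp(−kt) − exp(−ka·t).

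| t (h) | 0 | 0.5 | 1 | 2 | 4 | 6 | 8 | 9 | 10 |
|---|---|---|---|---|---|---|---|---|---|
| C | 0 | 0.2511 | 0.3826 | 0.4561 | 0.3576 | 0.2339 | 0.1470 | 0.1161 | 0.0915 |

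**Linear trapezoid to 6 h.** 0.0628 + 0.1584 + 0.4194 + 0.8137 + 0.5915 = 2.0458.

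**Added by the late sample.**

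- 8 h: 2 × (0.2339 + 0.1470)/2 = 0.381, and 0.381/2.0458 = 18.6%.
- 9 h: 3 × (0.2339 + 0.1161)/2 = 0.525, or 25.7%.
- 10 h: 4 × (0.2339 + 0.0915)/2 = 0.651, or 31.8%.

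**Other rules and steady state.** Exact single-dose integration uses AUC(0–T) = (1 − exp(−kT))/k − (1 − exp(−ka·T))/ka. For 12-hourly steady state, each exponential in C(t) is divided by 1 − exp(−12 × its rate constant).

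| Increase over AUC to 6 h | 8 h | 10 h |
|---|---|---|
| Single dose, linear trapezoid | 18.6% | 31.8% |
| Single dose, linear-up/log-down | 18.4% | 29.9% |
| Single dose, exact | 18.0% | 29.2% |
| Steady state, linear trapezoid | 18.0% | 30.8% |
| Steady state, exact | 17.5% | 28.4% |

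**Sensitivity (8 to 10 h, both dosing states, exact and linear trapezoid).** Half-life 2.3 h: 16% to 28%. Half-life 3.9 h: 20% to 38%. Effective half-life 4 to 6 h: 20% to 46%. At 2.9 h, with the Protocol's 60-minute window taken to its edges (7 and 11 h): about 10% to 37%.

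**Is the late sample likely to be quantifiable?** The model puts it at 32% of Cmax at 8 h (0.1470/0.4561) and 20% at 10 h (0.0915/0.4561). It should usually be quantifiable, so the last sample taken and the last quantifiable sample should usually coincide.

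**Effect on a small cohort.** With three subjects of equal exposure, one 10 h sample raises the mean AUC0-t by 31.8%/3, about 10.6%.

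**The case against.** AUC to the last quantifiable concentration is a standard output, and nothing primary depends on it: no MTD or efficacy decision uses AUC0-t. For Phase 1 cohorts the SAP already derives AUC0-12h and CL/F on Cycle 1 Day 8, and optional population modelling can accommodate uneven sampling. This stands and limits the point to AUC0-t. It does not remove it: AUC0-12h is not planned at the other visits or available in Phase 2, and without the late sample it must itself be extrapolated from 6 h.

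Three stronger readings are tempting, and the documents do not support them.

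- *That visit comparisons within a subject are distorted.* The definition fixes the end time within a subject across all treatments. That can be read as one common t per subject, which would protect such comparisons. It does nothing between subjects. The full Cycle 2 Day 1 profile is also only in the Amendment 7 Protocol; the SAP was written to Amendment 1 and plans none there.
- *That the shift exceeds a real dose effect.* One 10 h draw in three subjects moves the mean by about 10%. The smallest proportional epacadostat dose step, 75 to 100 mg, is 33%. In Protocol Table 3, geometric mean AUC0-t rises from 4.97 to 8.88 between 100 and 300 mg BID, or 79%. The AUC0-t SD there is 34% to 43% of the mean in six of eight groups, so the standard error of a three-subject mean is about 20% to 25% (34/√3 to 43/√3). The shift lies within that noise.
- *That the SAP plans dose or visit comparisons of AUC0-t.* Section 7.5.3 plans estimation only, 7.5.5 describes listings, and Appendix C has no PK table. The general rules in 5.1 and 5.2 still imply descriptive summaries by treatment group, and there the differing end times would matter.

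**Conclusion.** The concern holds for AUC0-t between subjects. Equal exposures can give values about 18% to 32% apart by linear trapezoid, or 18% to 29% by exact integration, depending on whether and when the optional sample was given.

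The size rests on a one-compartment model with half-life 2.9 h and Tmax 2 h. The upper figure depends on the integration rule, which the SAP does not name. It also assumes that the AUC0-τ entry is the intended definition of AUC0-t. Uptake of the late sample is not stated. If nobody gave it, the problem disappears. If everybody did, only the difference between 8 and 10 h remains.

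This is a minor point. It affects a secondary PK parameter, chiefly at Cycle 1 Day 1 and, under the current Protocol, in Phase 2. It is worth correcting because the samples for a common-interval AUC are already required.

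**What to change.** In SAP 7.5.3:

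1. Add AUC0-6h for every subject and visit with a full profile, and use it wherever AUC is summarized or compared across subjects, doses or visits.
2. Keep AUC0-t in the listings only.
3. Use the optional sample for half-life and AUC0-12h on Cycle 1 Day 8.
4. Align the symbol, so that the definition now printed against AUC0-τ appears under AUC0-t.

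The cost is a few lines of SAP text and one further noncompartmental output, with no new samples. At a common 6 h endpoint, the difference between subjects with identical exposure is zero by construction. The downside is that the summarized AUC covers a shorter interval and leaves out late concentrations that some subjects supplied. Because the 6 h sample has its own window (30 minutes in the SAP, 60 in the Protocol), some profiles will need a short interpolation or extrapolation to reach exactly 6 h.
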